10.2 Study Completion Criteria

A subject is considered to have completed the study when he/she has completed 8 months in the trial and received both treatment arms of the study. Enrolled subjects who withdraw from the trial prior to receiving study agent or who only complete one arm will be replaced; however, patients who complete only one arm will still be included in analysis.

10.3 Results Given to Participants and Physicians

Clinically relevant results will be transmitted to patients as part of this protocol. Participants are encouraged to remain in contact with the responsible investigators regarding advances in the field, and will be invited to enroll in pertinent future studies. Participants may request research publications resulting from this protocol. Medical care after study completion will occur with

the primary treating physician and rheumatologist. Results of tests will be shared with the medical provider and patient if consider medically/clinically relevant.

10.4 Blinding, Packaging, Labeling and Storage

Study agent (15 mg pioglitazone or placebo) will be packaged in identical vials each containing 300 capsules. Both study agents will be blinded using identical-looking capsules prepared by a vetted vendor selected by the NIH Pharmaceutical Development Service (PDS). Each vial will be labeled with a treatment number specific to the subject. A 300 capsule (one vial) supply of study agent will be given to each subject at enrollment at the baseline visit and at month 5. The amount of study agent dispensed will be sufficient to last from baseline to month 3, and from month 5 to month 8. The randomization code will be provided by the Clinical Center Research Pharmacy, as mentioned above. Emergency unblinding will occur in the case of a serious adverse event (SAE) that is considered potentially secondary to the drug. Unblinding will be performed by PDS. Only the pharmacists will be unblinded throughout the trial. The subjects, the investigators, and the study site staff will remain blinded to study medication assignment during the entire study period. Compliance with study treatment and pill counts will be performed by the research nurse/study coordinator and this information will be provided to PDS as well.

11 DATA ANALYSIS

The study measures the primary and secondary outcome variables at 4 time periods in each subject. We will begin with a univariate investigation of the outcomes to check for outliers and distributional properties followed by an assessment for carryover effects. The analysis of the study will be conducted using a 2-period cross-over model by comparing matched pair differences for the subjects in the first sequence with those in the second sequence. We expect this analysis will indicate no difference between the groups. If we find no carry over effect the modeling will continue without controlling for sequence. If we do find a sequence effect we will account for it in our models. The analysis will be based on a repeated measures analysis accounting for treatment and period effects and incorporating the two baseline measures. We will use a generalized linear model and a Generalized Estimating Equations (GEE) framework with two dummy variables, one indicating treatment condition and the other indicating the baseline condition (the omitted or the reference condition is Placebo). We will use an unstructured covariance matrix and robust standard errors. The primary parameter of interest is the regression coefficient for the treatment condition (a contrast between the placebo and pioglitazone). This approach is attractive because it can handle non-normal and categorical outcomes. The analysis is robust to model mis-specification¹⁵⁴.

The approach used in testing the hypothesis under the three specific aims will be similar. For Specific Aim 1, we will perform a separate analysis for each outcome variable: CAVI/Sphygmocor, PAT and FDG/CT. We will also perform secondary analysis using serum and cellular CV biomarkers. Our first analysis will be a randomization based analysis with no

covariates other than treatment and period effects. There are several confounding variables, especially medications that could contribute towards the variation in the outcome. We will expand the regression models by including them as predictors. If the number of confounding variables is large, we will use investigate a propensity score matching analysis. For Specific Aim 2, we will define a dichotomous clinical endpoint measuring lupus disease activity. Patients achieving an improvement of the SLEDAI-2K by 20%, a significant improvement in PGA and the absence of a BILAG 2004 A or B flare will be considered to have improved. Others will be defined as not having improved. The analysis for this score will be similar to the one proposed for Specific Aim 1. A GEE model will be used to assess treatment differences. We will also investigate the separate effects of each of these measures. The same approach used in Aim 1 will be taken for confounding variables using regression or propensity score adjustment. We will begin the investigation of Aim 3, assessment of innate and adaptive immune abnormalities in SLE, with a graphical analysis of the variables. We use multivariate methods to determine good summary measures of the various factors and compare the two treatments using the same models as defined for Aims 1 and 2.

Our primary analysis will be performed as an intent-to-treat analysis. If the subjects providing complete data are systematically different from those who dropped out, then the estimates based only on completers will be biased. We will investigate adjusting for differences in the populations who are completers and noncompleters and will consider multiple imputation to impute the missing values. Before the database is locked and final analysis performed, violations will be assessed on a case-by-case basis by the PI to determine if the medication change was such that it would adversely affect the study results. If changes may adversely affect data interpretation, subjects will be dropped from final analysis. A post hoc analysis of disease activity, measured by SLEDAI-2K, will be adjusted for burst steroids in excess of that permitted by the protocol. Analysis of prednisone doses, daily and cumulative will also be included.

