8 STUDY DESIGN AND METHODS

This will be a single-center, randomized, double-blind, placebo-controlled, crossover, proof-of-concept treatment trial enrolling 100 SLE patients including replacements due to screen failures and withdrawals. If a patient drops out of the study before completion both arms, another patient may be enrolled so that up to 75 patients complete the study. They will be treated for 3 months with 45 mg daily pioglitazone or placebo, undergo an 8 week washout period, then undergo crossover to the other arm for 3 additional months. Throughout the study, functional, anatomical and blood biomarkers of vascular damage, atherosclerosis risk and SLE activity will be collected. Pioglitazone has been chosen over rosiglitazone because it appears to have a significantly better safety profile regarding CV effects and lipid profile alterations⁹³, based on our experience in the rheumatoid arthritis (RA) trial⁵ and the small pilot study published by

another group that showed improvement in some metabolic parameters in SLE⁹², as well as our preliminary data which indicate improvement of vasculogenesis by pioglitazone but not rosiglitazone⁹⁴ in human SLE. We also have significant experience using this drug due to the recently completed clinical trial in RA³. The dose and study time period have been selected based on pioglitazone's macrovascular protective effects⁷⁴ and to allow detection of meaningful changes in endothelial function and disease activity, respectively. This is also based on the dose and study time period used in the RA trial, which showed significant effects on arterial stiffness, metabolic parameters, inflammatory markers and RA disease activity⁵.

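### The planned GEE names no small-sample correction; in its usual form a 5% test would run at about 6-7% in the main analyses and about 7-8% in PET/CT

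*Combined protocol and SAP*

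**What the plan says.** Section 11 (Data Analysis) fits a GEE to all visits: "The study measures the primary and secondary outcome variables at 4 time periods in each subject". The mean model is specified "with two dummy variables, one indicating treatment condition and the other indicating the baseline condition", and the first analysis has no "covariates other than treatment and period effects". On variance, the plan says "We will use an unstructured covariance matrix and robust standard errors". On the estimand, "The primary parameter of interest is the regression coefficient for the treatment condition", that is, pioglitazone against placebo.

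The same approach covers all of Aim 1: "we will perform a separate analysis for each outcome variable: CAVI/Sphygmocor, PAT and FDG/CT". Section 8 sets the size by allowing replacements "so that up to 75 patients complete the study". Sections 9.5.1 and 9.5.3 limit PET/CT to 15 patients per initial allocation, scanned at baseline and month 3 only.

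Sections 11 and 11.1 give no small-sample correction, no choice between a normal and a t reference, and no significance level or sidedness.

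**The concern.** The sandwich variance is justified for large numbers of patients. In smaller samples it tends to be too small even when the mean model is right, because fitted residuals are smaller than true errors. Here the GEE weights also come from an unstructured 4x4 matrix with 4 x 5 / 2 = 10 parameters, estimated from about 75 patients, and the usual formula ignores that estimation. The plan's argument that the method tolerates a misspecified model concerns large-sample validity and does not address this bias.

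At stake are the error rate and interval width for both primary vascular outcomes (arterial stiffness and PAT) and, more so, for PET/CT. Section 7 says the trial should show which surrogate outcomes merit use in later lupus studies, so a false positive here could be carried forward.

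**Working it through.** **Inputs from the documents.** Four visits (months 0, 3, 5, 8); 1:1 sequences (section 9.4); up to 75 completers (section 8); 100 recruited with dropout of 20% or more (section 11.1); one-arm completers kept (section 10.2); PET/CT in 15 + 15 patients at two visits.

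**Assumed.** Two-sided 5% level, uncorrected sandwich, critical value 1.96.

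**The plan's own figure.** There is no stated error rate or power to reproduce. On numbers, 100 x 0.80 = 80 completers, 75/0.80 = 94 entrants (rounded up) and 75/0.75 = 100. The figure 94 is derived and does not appear in the plan. The range 75 to 94 was examined.

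**Analytic check with no weights to estimate.** Take a two-group comparison of differences with p = 2 mean parameters. The uncorrected variance has divisor n where n - p is needed, so the standard error shrinks by f = sqrt((n - p)/n). The true rate is 2 x P(t with n - p df > 1.96 x f):

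- n = 75: f = sqrt(73/75) = 0.987; 1.96 x f = 1.934; rate 5.7%.
- n = 94: f = sqrt(92/94) = 0.989; 1.96 x f = 1.939; rate 5.6%.
- n = 30: f = sqrt(28/30) = 0.966; 1.96 x f = 1.894; rate 6.9%.

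Estimating the unstructured weights can add to this.

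**Simulation under no treatment effect.** The model had treatment, baseline condition and period. The runs had 6,000 to 20,000 trials per setting, with Monte Carlo error of about 0.2 to 0.3 points. Settings varied the visit correlation, a sequence term, 20% dropout, five covariates and a skewed outcome.

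| Analysis | 75 to 94 patients | PET/CT, 15 v 15 |
|---|---|---|
| GEE, uncorrected sandwich, normal reference | 5.8-7.1%, mostly 6-7% | 6.9-8.0% without a group term; mostly 6.5-6.9% with one (one set 6.9-7.4%) |
| GEE, Mancl-DeRouen sandwich, t reference | 5.1-6.2% | 4.1-5.2% |
| Difference regression with baseline difference, t reference | 4.7-5.4% | not applicable |
| t-test on change | not applicable | 5.1% |

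For normal outcomes the mean robust standard error was 0.94-0.97 of the true value at 75 to 94 patients and 0.92-0.96 for PET/CT. Intervals are thus about 3-6% and 4-8% too narrow from this source.

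**Power.** With constant correlation 0.7, N = 75 and an assumed standardised effect of 0.25, the planned GEE gave 82.1% and the difference regression 79.9%, a gap of 2.2 points. With correlation decaying over visits (AR(1)), the planned GEE gave 70.6%, Mancl-DeRouen with t 67.5%, and the difference regression 63.2%. Of that 7.4-point gap, 67.5 - 63.2 = 4.3 points remain after the correction. A separate AR(1) run (0.7, N = 75) that equalised type I error gave 64.4% for the GEE against 59.6% for the difference regression.

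**The case against.** **The plan does not say the sandwich is uncorrected.** This stands as a limit. A Mancl-DeRouen estimate is itself a robust standard error, and neither a normal reference nor a 5% level is written down. A reader might infer that the plan commits to an inflated 5% test. It does not: it leaves that test open, in its most usual form.

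**The effect is small for a proof-of-concept trial.** Also fair. The excess is about 1 to 2 points, and in one set of runs a t reference alone brought it to 6.0% at 75 and 5.7% at 94. That argues for a modest rating; it does not make the fix unnecessary.

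**Section 11 also mentions matched-pair differences between sequences and a randomization-based first analysis.** If either were the primary test with a t reference, the problem would largely disappear. But the matched-pair comparison sits with the carryover check, the second phrase is not developed, and the parameter named as primary is the GEE coefficient.

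**The PET/CT figure depends on an unstated model.** Correct. With only two visits the four-visit model cannot apply literally, and a group term lowers the inflation. PET/CT is also a subset measure, not a named primary outcome.

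**The GEE's extra power is only excess error.** A reader might infer this from the constant-correlation result, but it is not supported. Sections 10.2 and 11.1 keep patients with partial data, and under decaying correlation the four-visit weighting gives a real gain.

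**Conclusion.** The concern holds as a modest one that should be fixed. In its usual form, and at an assumed two-sided 5% level, the planned analysis tests at about 6-7% with 75 to 94 patients, which is 20-40% more false positives than intended. PET/CT tests at about 7-8% (40-60% more), or about 6.5-7% with a group term. Intervals are slightly too narrow.

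This rests on an uncorrected sandwich with a normal reference, inferred from the plan's silence, and on mainly normal simulated outcomes. The figures come from purpose-written code and were not confirmed with a packaged GEE routine. The binary Aim 2 endpoint was not simulated, so no size is claimed for it.

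**What to change.** State the significance level, sidedness, variance estimator and reference distribution in section 11, and change the test as follows.

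- **Continuous crossover outcomes.** Use a REML mixed model with treatment, period and baseline condition, unstructured covariance and Kenward-Roger degrees of freedom. It keeps the four-visit weighting and partial data. This option was not simulated here and should be checked before adoption.
- **Simple alternative.** Regress the month 3 minus month 8 difference on sequence, with the month 0 minus month 5 difference as covariate and a t reference. It holds about 5%. It is not equivalent to the four-visit model: it needs complete pairs and drops information carried by the other visit combinations. It lost about 5 to 7 points of power under decaying correlation.
- **PET/CT, and wherever GEE is kept.** Use the Mancl-DeRouen sandwich with a t reference. This gives about 4-5% for PET/CT. For the main outcomes it leaves about 5.5-6%, so it is second choice there. State whether the PET/CT model has a group term.

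The cost is a few SAP sentences and a software option, plus about 2 points of apparent power under constant correlation. No visit, measurement or patient is added.

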7 OBJECTIVES

The major goal of the proposed research is to assess the effect of a targeted pharmacotherapeutic intervention – the administration of the PPAR- γ agonist pioglitazone – in SLE on:

- vascular endothelial function (primary endpoint), a predictor of CV risk
- SLE disease activity (secondary endpoint).

This randomized clinical trial, with a modest sample size, can both serve as a “proof of concept” study for the potential utility of TZDs in SLE, and inform us on which surrogate outcomes or biomarkers may be useful in future lupus studies aimed at CV/immunomodulatory outcomes.

Aim 1: To conduct a randomized, double-blind, placebo controlled, crossover, proof-of-concept clinical trial in adult SLE patients comparing the effects of pioglitazone vs. placebo on vascular endothelial function and blood vessel inflammation. Primary outcome measures will be large

vessel arterial stiffness, measured either by cardio-ankle vascular index (CAVI) or pulse wave velocity (PWV, assessed by Sphygmocor) (both tests to assess large vessel arterial stiffness), and assessment of microvascular peripheral arterial tone (PAT). Secondary outcome measures of atherosclerosis risk and metabolic disturbances will include proinflammatory HDL (piHDL) levels and HDL cargo, lipoprotein function, lipid profile and insulin resistance and EPC phenotype and function. In addition, modulation of arterial inflammation will be assessed in a subset of patients by neck to groin fluorodeoxyglucose positron emission tomography CT (FDG PET/CT).

Hypothesis 1: Endothelial function and arterial compliance will significantly improve in SLE patients treated with pioglitazone when compared to placebo, while arterial inflammation will decrease.

Hypothesis 2: Pioglitazone will alter HDL cargo function, decrease proinflammatory HDL levels and insulin resistance, and improve markers of vascular repair in SLE.

Aim 2: To assess the ability of pioglitazone to reduce SLE disease activity, when added to standard lupus care, as assessed by the SLEDAI-2K disease activity index (SLEDAI-2K), lack of A or B flares on the British Isles Lupus Activity Group (BILAG 2004) score, and physician's global assessment (PGA) (See Appendix sections 2,3,7). Serological markers of SLE activity and various cytokines considered important in lupus pathogenesis will also be quantified.

Hypothesis 3: SLE Disease activity will decrease in SLE patients when treated with pioglitazone vs. placebo.

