12.2.2.4 FDG/PET/CT

The NIH Clinical Center PET department uses only commercially available FDG.

The effective radiation dose from 10 mCi FDG is approximately 0.62 rem. Thus the total radiation from one FDG scan and a transmission CT scan is 1.32 rem. In addition to any radiation concern, there could be psychological distress caused by an incidental finding of asymmetric FDG uptake that would likely necessitate additional investigation to exclude cancer or other lesions (see below).

Additional minimal risks include bleeding or bruising at the venous site of FDG administration. We have provided radiation dosimetry at the end of this protocol. This procedure will not be performed more often than twice per patient during the 8 month duration of this trial and will be performed in 30 out of the 70 patients. Overall, minimum exposure will be 0 rem/year (only

vascular function tests but no imaging) and maximum exposure will be 2.64 rem/year, which is within the annual exposure limits.

Participants may experience mild claustrophobia from the PET CT. The participant will be able to notify the technician throughout the scan if he/she needs to come out of the scanner.

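### Do two primary vascular outcomes with no stated alpha or success rule inflate the false-positive risk?

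*Combined protocol and SAP*

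**What the plan says.** Section 7 (Objectives) lists the primary endpoint as a construct: "vascular endothelial function (primary endpoint), a predictor of CV risk". Aim 1 in the same section turns it into two primary outcome measures. One is large "vessel arterial stiffness, measured either by cardio-ankle vascular index (CAVI) or pulse wave velocity"; the other is PAT. FDG-PET/CT is described apart from these, in a subset of patients, so the primary count is two.

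Hypothesis 1 joins the constructs: "Endothelial function and arterial compliance will significantly improve in SLE patients treated with pioglitazone when compared to placebo". Section 7 also gives the trial's purpose as proof of concept, and says that it should "inform us on which surrogate outcomes or biomarkers may be useful in future lupus studies".

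Section 11 (Data Analysis) makes the GEE treatment coefficient the primary parameter and applies it outcome by outcome: "we will perform a separate analysis for each outcome variable: CAVI/Sphygmocor, PAT and FDG/CT". Sections 11 and 11.1 give no alpha, sidedness, order, alpha split, or statement on whether one or both primaries must be positive. Section 11.1 gives no power percentage, effect size or standard deviation either.

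On numbers, section 8 plans 100 enrolled, and says "another patient may be enrolled so that up to 75 patients complete the study". The radiation-risk text in section 12.2.2.4 refers to "30 out of the 70 patients".

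**The concern.** With two declared primaries and no rule, the same data could be called positive or negative. Section 8.1.1 makes a split result plausible: in the investigators' rheumatoid arthritis trial, pulse wave velocity improved on pioglitazone but PAT did not. If that happened again, a reader who accepts either outcome would call the trial a success, and a reader who holds to the conjunction in Hypothesis 1 would call it a failure. If the choice were made after unblinding, the more generous reading could win, and its false-positive rate would be up to about twice that of a single test. Holding the declared primary outcomes to a written decision rule is ordinary practice, so the omission draws attention.

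**Working it through.** **The plan's own figures.** There is no error rate or power figure to reproduce, because alpha, power, effect size and standard deviation are all absent. Everything below assumes two-sided 5% per test and a paired t-test (n − 2 degrees of freedom) as an approximation to the planned GEE. Effects d are within-patient standardised differences, and n = 75 is the upper limit on completers in section 8.

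**Reading 1: either outcome suffices, no adjustment, both truly null.** For independent outcomes the chance of at least one significant result is 1 − (1 − 0.05)² = 0.0975. Counting only false improvement, it is 1 − (1 − 0.025)² = 0.0494, against 0.025 for one test. Bivariate normal values with correlation:

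| Correlation | At least one significant | At least one false improvement |
|---|---|---|
| 0 | 9.75% | 4.9% |
| 0.3 | 9.5% | 4.8% |
| 0.5 | 9.1% | 4.5% |
| 0.7 | 8.3% | 4.2% |
| 0.9 | 7.0% | 3.5% |

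**Reading 2: both required.** A false overall claim needs both tests to err, or one to err while the other is truly positive, so it cannot exceed the single-test rate. There is no inflation. The price is power. With stiffness d = 0.4 (power 0.928) and independent outcomes:
- PAT d = 0: 0.928 × 0.025 = 0.023
- PAT d = 0.2: 0.928 × 0.401 = 0.37
- PAT d = 0.3: 0.928 × 0.727 = 0.67
- PAT d = 0.5: 0.928 × 0.990 = 0.92

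**Reading 3: a separate conclusion on each outcome.** Each claim keeps its own 5% level. No trial-level verdict is made, so there is none to inflate. This matches the separate analyses in section 11 and the purpose in section 7.

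**How far the rule could matter.** With stiffness d = 0.4, PAT d = 0 and independence, success is 1 − (1 − 0.928)(1 − 0.025) = 0.93 under Reading 1 and 0.023 under Reading 2. Under Reading 3 the report would be that stiffness improved and PAT did not, which describes the data without a contest over labels.

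**What a formal rule would cost (n = 75).**
- Holm: testing at 2.5% instead of 5% lowers power from 0.727 to 0.622 at d = 0.3, from 0.928 to 0.878 at d = 0.4, and from 0.990 to 0.978 at d = 0.5. That is a loss of at most about 10, 5 and 1 points.
- Fixed sequence, stiffness then PAT: stiffness keeps full power. If stiffness is null and PAT has d = 0.3 to 0.5, a PAT improvement is claimable in only about 2% to 2.5% of trials, against 62% to 98% under Holm.
- Both required: no alpha cost, but success is capped by PAT as shown above.

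**PAT sample size.** Exclusion criterion 17 in section 9.3 keeps patients with severe Raynaud's phenomenon, finger ulcers or gangrene from EndoPAT testing, so n for PAT may be below n for stiffness. The documents give no proportion. If 10% or 20% of 75 were untested (assumed; n about 68 or 60), PAT power at d = 0.3 falls from 73% to 68% or 63%, and the both-required figure falls from 67% to 63% or 58%.

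**The case for a change.** The strongest case for a change is that the omission is real, repair takes a sentence, and a proof-of-concept label does not say what a positive result is. Hypothesis 1 predicts significant improvement, which cannot be confirmed or refuted without a level and a rule. The conventional 5% would supply a level but not an order or an either/both rule. The earlier arthritis result makes a split outcome plausible. Section 11.2 has the monitoring committee review unblinded data every six months, and Table 4 lists interim analyses, so any rule is better fixed early.

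Much of this stands as description: two primaries are named and no rule is given. It does not establish harm. The doubling belongs to an either-suffices rule found nowhere in the protocol. Section 10.4 keeps investigators blinded for the whole study, and the unblinded reviewers under section 11.2 are not affiliated with it, so the remaining exposure is a choice of rule after final unblinding. A reader who has both results and the wording of section 7 can see through such a choice.

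Nor is there one obvious sentence to add. The candidate rules exclude one another. Stiffness first follows the arthritis evidence, but section 7 calls the primary endpoint endothelial function, and section 8.1.1 describes PAT as the test of endothelial function; that order could leave the named construct unclaimable. Stating 5% would also leave open what the interim looks are for, which is a separate question.

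**Conclusion.** No change to the plan is called for. The omission is genuine, but it is a detail that analysts can fill sensibly: report both primary outcomes, each with its estimate, interval and two-sided test, and claim no overall success on one alone. On that reading, or under the conjunction in Hypothesis 1, no individual claim carries more than its nominal error. The worst case, 7.0% to 9.75% for any false significant result and 3.5% to 4.9% for false improvement, depends on a rule the documents do not state. Strict family-wise control matters less in a proof-of-concept trial intended to sort surrogate outcomes, and each way of imposing it involves a trade-off on which statisticians could fairly differ: up to about 10 points of power per outcome, or near-total loss of a PAT claim when stiffness fails, or success limited by PAT.

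The sizes rest on assumed values throughout: two-sided 5%, d from 0 to 0.5, correlation from 0 to 0.9, 75 completers and a paired t approximation. PAT power would be somewhat lower if some patients skip EndoPAT. Section 11.1 also expects partial data to be used, so the analysed number may differ from 75. The conclusion does not turn on any of these values.
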